#### 9.6. Columbia Suicide Severity Rating Scale (C-SSRS)

The C-SSRS is routinely used to quantify the severity of suicidal ideation and behavior. Both the ideation and behavior subscales are sensitive to change over time.

Two versions of the C-SSRS will be used in this study: the Screening version and the Since Last Visit version. The Screening version of the C-SSRS assesses lifetime suicidal ideation and behavior. The Since Last Visit version of the C-SSRS assesses suicidal thoughts or behaviors the participant may have had since the last time the C-SSRS was administered.

At the screening visit, the C-SSRS Screening version will be administered. At all subsequent visits, the C-SSRS Since Last Visit version will be administered.

The C-SSRS includes "yes" or "no" responses for assessment of suicidal ideation and behavior as well as numeric ratings for severity of ideation, if present (from 1 to 5, with 5 being the most severe). Assign a score of 0 if no ideation is present.

Suicidal Ideation items include:

Category 1 – Wish to be Dead

Category 2 – Non-specific Active Suicidal Thoughts

Category 3 – Active Suicidal Ideation with Any Methods (Not Plan) without Intent to Act

Category 4 – Active Suicidal Ideation with Some Intent to Act, without Specific Plan

Category 5 – Active Suicidal Ideation with Specific Plan and Intent

Suicidal Behavior items include:

Category 6 – Preparatory Acts or Behavior

Category 7 – Aborted Attempt

Category 8 – Interrupted Attempt

Category 9 – Actual Attempt (non-fatal)

Category 10 – Completed Suicide

Self-injurious behavior without suicidal intent is also a C-SSRS outcome (although not suicide-related) and has a binary response (yes/no).

#### **Endpoints:**

Composite endpoints based on the above categories are defined below:

- Suicidal **ideation**: A "yes" answer at any time during treatment to any one of the five suicidal ideation questions (Categories 1-5) on the C-SSRS.
- Suicidal **behavior**: A "yes" answer at any time during treatment to any one of the five suicidal behavior questions (Categories 6-10) on the C-SSRS.

• Suicidal **ideation or behavior**: A "yes" answer at any time during treatment to any one of the ten suicidal ideation and behavior questions (Categories 1-10) on the C-SSRS.

Baseline is defined as the most severe ideation and behavior reported in the past 6 months prior to the first dose of study drug. Suicidality data collected on the C-SSRS will be listed for all participants with at least one occurrence of suicidal ideation or behavior during treatment. Tables will include results from the Suicidal Ideation and Suicidal Behavior sections of the C-SSRS. Frequencies and percentages of participants with a response of "Yes" at any point as well as by study visit on the Suicidal Ideation and Suicidal Behavior items will be summarized by treatment received.

Additionally, shifts of whether participants experienced suicidal ideation, behavior, or both from pre-treatment to post-treatment will be summarized in a shift table. An additional shift table of maximum ideation from pre-treatment to post-treatment will also be provided.

All C-SSRS data will be listed.

#### 9.7. Prior and Concomitant Medications

Medications used in the study will be summarized as follows:

- Medications that started prior to the first dose of study drug will be considered prior medications whether they were stopped prior to the first dose of study drug.
- Any medications continuing or starting post the first dose of study drug will be concomitant.
- If a medication starts prior to the first dose and continues after the first dose of study drug, it will be considered both prior and concomitant.

[figure not shown]
Summaries of medications and therapies will be presented in tabular form using the Therapeutic Indication (ATC level 3) as an upper classification and the preferred drug name as a lower classification level. All medications will be summarized by the number and percentage of participants taking each medication and sorted by descending counts (overall) in the upper classification term and the lower classification term within the upper. For each participant, the medication will be counted only once within the upper classification level and only once within the lower classification level.

Prior and concomitant medication listings will include start and stop dates, medication name, route, dose, dose frequency, and reason for use.

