10.3 Concomitant Medications and Other Restrictions

All medications mentioned in the exclusion criteria (Section 9.3) are expressly prohibited at any time during the study. Exceptions to the list of excluded medications may be made on a case-by-case basis if discussed and approved by the Medical Monitor in advance. Intake of drugs or substances potentially involved in clinically significant CYP3A4 or P-gp mediated drug interactions with CT1812, within 4 weeks or five half-lives of the interacting drug prior to administration of CT1812 and throughout the course of the study. Grapefruit juice should be avoided in the two weeks prior to dosing and throughout the course of the study. See Appendix A for a list of these prohibited substances.

Participants may be on stable doses (at least 30 days prior to screening) of an acetylcholinesterase inhibitor and/or memantine and continue these medications during the study. Participants may be on a stable dose (at least 60 days prior to screening) of an SSRI antidepressant and may continue this medication during the study.

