#### 2.2. Study Endpoints

#### 2.2.1. Safety Endpoints

The safety endpoints of this study include the following:

- The incidence and severity of adverse events (AEs).
- The change in usage of concomitant medications.
- Changes in vital signs.
- Changes in physical exam findings.
- Changes in electrocardiogram findings.
- Changes in clinical laboratory testing (serum chemistry, hematology, urinalysis).
- Changes in the Columbia Suicide Severity Rating Scale (C-SSRS).

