#### 6.1.9. Data Adjustments/Handling/Conventions

All collected data will be presented in listings. Data not subject to analysis according to this plan will not appear in any tables or graphs but will be included only in the data listings.

All P-values will be displayed in four decimals and rounded using standard scientific notation (e.g., 0.XXXX). If a P-value less than 0.0001 occurs, it will be shown in tables as < 0.0001. If a P-value greater than 0.9999 occurs, it will be shown in tables as > 0.9999.

Adverse events and medical history will be coded using the latest version of the Medical Dictionary for Regulatory Activities (MedDRA) thesaurus available at the time of database lock.

Prior and concomitant medications will be coded using the latest version of World Health Organization - Drug Dictionary Enhanced (WHO-DDE) available at the time of database lock.

A treatment-related AE is any AE with a relationship to the study drug of probable or possible.

If it is necessary to calculate a participant's age from the (partial or complete) date of birth

(DOB) and the date of the Baseline Visit, the floor function will be used to ensure the participant has an integer age.

If partial AE dates or partial medication dates occur, the convention for replacing missing dates for the purposes of calculating derived variables is as follows:

For partial AE and medication start dates:

- If the year is unknown, then do not impute the date but instead assign a missing value.
- If the year is known, but the month or month and day is unknown, then:
  - o If the year matches the year of first application date and the end date (if present) is after first dose date, or AE/medication is ongoing, then impute as the month and day of the first application date. If this produces a date after the AE/medication end date, assign 01 January.
  - o Otherwise, assign 01 January.
- If the year and month are known, but the day is unknown, then:
  - o If the month and year match the month and year of the first dose date, then impute as the day of the first dose date. If this produces a date after the AE/medication end date, assign 01.
  - o Otherwise, assign 01.

For partial AE and medication end dates:

- If the year is unknown, then do not impute the date but assign as missing value.
- If the year is known but the month or month and day is unknown, then:

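### SAP 9.7 tabulates only who ever took each medication, so the listed safety endpoint of change in concomitant medication use is not estimated (minor)

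*SAP*

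**What the plan says.** Safety is the primary objective. Protocol 6.2.1 and SAP 2.2.1 each list seven safety endpoints, one of which is "The change in usage of concomitant medications".

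SAP 9.7 is the only section that analyses it. A drug begun before the first dose is prior. For the other category the rule is: "Any medications continuing or starting post the first dose of study drug will be concomitant". A drug that spans the first dose belongs to both categories: "it will be considered both prior and concomitant". The tabulated statistic is a count: "All medications will be summarized by the number and percentage of participants taking each medication". The levels are ATC level 3 class and preferred drug name, with this counting rule: "For each participant, the medication will be counted only once within the upper classification level and only once within the lower classification level". Start and stop dates, dose, frequency and reason for use appear in listings only.

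SAP 6.1.9 has one partial-date rule for adverse events and medications together. If only the year of start is known, it is the year of first dose, and the drug is ongoing or ended after first dose, "then impute as the month and day of the first application date". If month and year are known and match those of first dose, the start is set to the first-dose day.

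Protocol 9.2 requires treatment of other chronic conditions to have been stable for at least 30 days before screening. Protocol 10.3 adds: "Participants may be on stable doses (at least 30 days prior to screening) of an acetylcholinesterase inhibitor and/or memantine".

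**The concern.** The endpoint is a change, but the planned statistic is prevalence of use. Other safety endpoints in the SAP have a time or change dimension. Laboratory values get changes and shift tables (9.2.1), vital signs get changes (9.3), ECG and physical findings are shown by visit (9.4, 9.5), and the C-SSRS gets by-visit counts and shifts (9.6). Adverse event tables are limited to treatment-emergent events (9.1). Medications have no visit, change or shift display, and SAP 10 does not say that the endpoint was dropped or redefined.

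What is at stake is a supporting safety signal. Protocol 4.3 reports nausea, vomiting, headache, fatigue and depression more often at the highest dose of the earlier 28-day study in Alzheimer's disease. Treatment newly started for such events is what a change-in-use endpoint could pick up. Because eligibility favours people on stable chronic treatment, many entries in the concomitant rows will be drugs carried over unchanged.

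**Working it through.** The documents state no figure for this endpoint, so there is none to reproduce. The check applies the SAP rules to assumed counts. Only the 48 per arm is from the plan.

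**1. What the table rows contain.** For one drug in one arm of n participants, let P be users who started and stopped before first dose, B those who span it, and C those who start after it.

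- Prior row = (P + B)/n
- Concomitant row = (B + C)/n
- Difference of the rows = (C − P)/n

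New starts (C) do not appear alone. Stops on treatment occur within B or C and change neither row. A dose change of the same drug changes neither row, because each preferred name counts once.

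| Assumed pattern, n = 48 | P | B | C | B users stopping on treatment | Prior row | Concomitant row |
|---|---|---|---|---|---|---|
| All continue | 0 | 20 | 0 | 0 | 20/48 = 41.7% | 20/48 = 41.7% |
| All stop on treatment | 0 | 20 | 0 | 20 | 20/48 = 41.7% | 20/48 = 41.7% |
| 5 stop before dosing, 5 start new | 5 | 15 | 5 | 0 | 20/48 = 41.7% | 20/48 = 41.7% |
| Same, and 15 stop on treatment | 5 | 15 | 5 | 15 | 20/48 = 41.7% | 20/48 = 41.7% |
| 8 start new | 0 | 12 | 8 | 0 | 12/48 = 25.0% | 20/48 = 41.7% |

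The first four patterns cannot be told apart. In the last, the rows differ by 8/48 = 16.7 points, which is (C − P)/n.

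**2. What the date rule does.** Assume a first dose on 15 Nov 2022.

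| Recorded start | Status | Start used | Category |
|---|---|---|---|
| 2022 | ongoing | 15 Nov 2022 | concomitant only |
| 2022 | ended 20 Dec 2022 | 15 Nov 2022 | concomitant only |
| Nov 2022 | ongoing | 15 Nov 2022 | concomitant only |
| 2022 | ended 1 Jun 2022 | 1 Jan 2022 | prior |
| Sep 2022 | ongoing | 1 Sep 2022 | both |
| 2021 | ongoing | 1 Jan 2021 | both |
| 10 Mar 2022 | ongoing | unchanged | both |
| year unknown | ongoing | missing | SAP 9.7 does not say |

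Only the first three rows can turn a pre-study drug into an apparent new start.

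**3. Which stable drugs this can reach.** A drug that met the 30-day rule began at least 30 days before screening, and screening ends at the latest on Day -1. It therefore began at least 30 + 1 = 31 days before Day 1. Two dates in one calendar month are at most 30 days apart, so the month-and-year branch cannot catch it. The year-only branch can, if the first dose falls on or after 1 February (1 January + 31 days).

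**The case against.** There is a fair case that the plan already does enough.

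- **Net change can be recovered.** Suppose 30/48 in each arm are carried-over users, with 4 new starters on placebo, 12 on active, and all starters previously non-users. The concomitant rows read 34/48 = 70.8% and 42/48 = 87.5%. Subtracting the prior row of 30/48 gives 4/48 = 8.3% and 12/48 = 25.0%, which are the new-start rates. This stands when P is zero and the two categories are tabulated separately, which SAP 9.7 suggests but does not state.
- **Randomisation helps.** B is fixed by first dose, so it is balanced between arms in expectation and the concomitant rows can be compared. This also stands, with noise. At 30/48 = 0.625 carried over, chance imbalance has a standard error of √(2 × 0.625 × 0.375/48) = 0.099, or about 10 points, against the 16.7-point difference in the example.
- **A second drug in a class is visible.** If 12 of the 30 class users add another drug of that class, the class row stays at 30/48, but the added drug appears in its own preferred-name row. This stands.
- **Other routes exist.** A new treatment would usually accompany an adverse event, and treatment-emergent events are tabulated by arm, severity and relationship. The listings hold the dates and reasons. The protocol synopsis promises only that concomitant medications will be summarised and listed, and its list of safety and tolerability measures omits them. All of this limits the importance of the gap.

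None of these points gives a tabulated count of starts, stops or dose changes.

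**Conclusion.** The gap is real and minor. Followed as written, the plan tabulates ever-use and does not estimate its own change endpoint. Starts are mixed with continued use, stops and same-drug dose changes are not tabulated, and at best a net figure can be derived. The date rule is a secondary defect that would also contaminate a new-start table.

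A reader might infer three stronger things that the documents do not support:

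- That the SAP moves pre-study drugs to Day 1 in general. It does so only for partial start dates in the first-dose year (ongoing, or ended after first dose) or in the first-dose month. The number of such records is unknown, and sites that verify 30-day stability may often hold fuller dates.
- That the overlap of prior and concomitant is the cause. It is not: counting spanning drugs in both is what makes the two rows comparable. With complete dates and the same categories, the tables would still be ever-use. The cause is the missing table.
- That the tables can show no change at all. A net difference is recoverable under the conditions above.

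The counts used here are illustrations and do not predict this trial's data. No inferential result depends on the point.

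**What to change.** Keep the existing tables. Add to SAP 9.7 one by-arm table of participants with at least one medication started, stopped or dose-changed after first dose. Show the three kinds of change separately, by ATC level 3 and preferred name, and say whether the count runs to last dose or to Day 210. State also that prior and concomitant use are tabulated separately.

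In SAP 6.1.9, for medications only, flag imputed partial start dates so that they do not count as new starts. The alternative is to impute the earliest date compatible with the recorded parts, unless the record shows an on-study start. Say how a drug with an unknown start year is classified.

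The cost is one descriptive table and a few sentences. Medications are recorded from screening through Day 210, so no new data are needed. The downside is that a few true on-study starts with partial dates will not be counted as new.

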#### 10. Changes from Planned Analysis

Four additional analysis populations are defined in this SAP but are not defined in the study protocol: All Subjects Population, mITT Population, Completers Population, and PK Population. These analysis populations have been added to enable the summary of disposition, the primary analysis of efficacy data (mITT), a sensitivity analysis of efficacy data (Completers), and analysis of PK data (PK). The Per-Protocol Population, also not defined in the study protocol but included in V1.0 of the SAP, was removed.

The score for the number cancellation item was originally set up to be derived within the clinical

study database, however prior to database lock, an error was discovered in the derivation of this item score. This error subsequently impacts the derivation of the ADAS-13 total score, which was also originally set up to be derived within the clinical study database. As a result, both the number cancellation item score and the ADAS-13 total score will be re-derived in the ADaM datasets for analysis purposes.

The Modified Hachinski total score and ADCS-ADL total score were originally calculated and entered into the study database by the sites. To ensure accuracy, it was decided to re-derive these total scores in the ADaM dataset.

Composite z-score scales (Cognitive Composite score; Memory composite score; Attention composite score; Executive Function composite score) are added to efficacy endpoints and their derivation are included in Section 6.1.8.

#### 11. Other Planned Analysis

#### 11.1. Pharmacokinetic and Pharmacodynamic Analysis

Pharmacokinetic parameters such as CT1812 cerebrospinal fluid (CSF)/plasma concentration ratio, and CT1812 plasma concentrations will be summarized by treatment or treatment and visit where applicable using the PK Population. Analysis of pharmacodynamic parameters are detailed in Section 8.8 (Biomarker Changes).

Statistical Analysis Plan, Sponsor Cognition Therapeutics, Inc. Protocol Number COG0201 PCN Number COGN187880

